Propranolol Rescue of Prolonged Labor (PROPEL)

A randomized, double-blind, placebo-controlled multicenter investigation of propranolol's effect on cesarean delivery rate among women with prolonged labor

Principal Investigator: [name], MSCE

Assistant Professor

Division of Maternal Fetal Medicine

Department of Obstetrics and Gynecology

[name]

[name]

[name]

Sub-Investigator(s): [name]

Clinical Fellow

Division of Maternal Fetal Medicine

[figure not shown]
Department of Obstetrics and Gynecology

Study Drug/Study Device: Propranolol hydrochloride

LIST OF ABBREVIATIONS

AE	Adverse event
DSMB	Data safety monitoring board
CD	Cesarean delivery
EFM	Electronic fetal monitoring
GBS	Group B streptococcus
HIE	Hypoxic ischemic encephalopathy
ICN	Intensive care nursery
ICU	Intensive care unit
IDS	Investigational drug service
IOL	Induction of labor
IRB	Investigational review board
IV	Intravenous
IVH	Intraventricular hemorrhage
NEC	Necrotizing enterocolitis
OB	Obstetric
RDS	Respiratory distress syndrome
SAE	Serious adverse event
VTE	Venous thromboembolism

STUDY SCHEMA

Study Summary

Title	Propranolol rescue of prolonged labor
Short Title	PROPEL
Methodology	Double-blind randomized controlled trial
Study duration	24 Months
Study Center (s)	Multi-center: Hospital of the University of Pennsylvania and Pennsylvania Hospital
Objective	To compare cesarean delivery (CD) rates in women given IV propranolol versus placebo for treatment of prolonged labor.
Number of Subjects	326
Diagnosis and Main Inclusion Criteria	
Meets criteria for prolonged labor:
 
 1. cervical dilation <6 cm after \geq12 hours with ruptured membranes and receiving oxytocin OR 2. cervical dilation >6 cm and <1 cm dilation change over \geq2 hours with ruptured membranes and receiving oxytocin 
AND
 
\geq16 years old, \geq 36 weeks gestation; Singleton gestation in vertex presentation; non anomalous fetus

Study Product (s), Dose, Route, Regimen	
IV Propranolol – 2mg; one possible repeat dose \geq2 hours later
 
Normal saline placebo- 2 mL; one possible repeat dose \geq2 hours later

Duration of administration	Eligible for maximum of one repeat dose \geq 2 hours after first until reaches 10cm dilation
Primary Outcome	Cesarean delivery
Statistical methodology	Intention to treat analysis, chi-square test for categorical variables, two-sample t-test for continuous variables

1 BACKGROUND AND RATIONALE

1.1 Condition Background

Since the 1980's, the rate of cesarean delivery (CD) in the US has climbed dramatically to its current rate around 33% of all deliveries.¹ While CD can be a life-saving procedure for both mother and baby, it also carries significant risks, both immediate and in future pregnancies. Currently, 34% of all CDs performed in the United States are for labor arrest, making labor arrest the most common indication for primary cesarean delivery.¹ The etiology of labor arrest is thought to be related to 3 primary factors – contraction strength or frequency, the size and position of the fetus, and the shape and space in the pelvis. Of these three etiologies, the most common cause of protracted labor is inadequate contraction strength and/or frequency. Additionally, this is the only truly modifiable etiology of labor arrest, so it is an important target for therapeutic intervention. Current standards for clinical management of labor arrest included artificial rupture of membranes and administering oxytocin to increase contraction strength and frequency. Even with these interventions, attempts to resolve labor arrest still often fail, up to 50% of the time.¹ There is a great clinical need for additional strategies to treat labor arrest and reduce the associated rates of CD and maternal morbidity. While some small prior studies have identified treatment with propranolol to have possible benefit in management of labor dystocia, others have not found the same results, likely due to heterogeneous populations being evaluated. Propranolol warrants further study to evaluate its effectiveness as an intervention for treatment of labor arrest.

1.2 Study Agent(s)/Devices Background and Associated Known Toxicities

Propranolol is a nonselective β -adrenergic receptor blocking agent that specifically competes with β -adrenergic receptor stimulating agents for available receptor sites, thereby decreasing chronotropic, inotropic, and vasodilator responses to β -adrenergic stimulation. $\beta 1$ adrenergic receptors are found primarily in the heart, where blockade of cardiac β -adrenergic receptors leads to a decrease in the activity of pacemaker cells and a decrease in A-V nodal conduction velocity. These actions lead to antiarrhythmic activity and control of ventricular rate. $\beta 2$ adrenergic receptors are found predominantly in smooth muscle, including vascular, bronchial, gastrointestinal, and uterine smooth muscle, where blockade of these receptors results in smooth muscle constriction.

Propranolol is contraindicated in 1) cardiogenic shock; 2) sinus bradycardia and greater than first degree block; 3) bronchial asthma; and 4) in patients with known hypersensitivity to propranolol hydrochloride. Adverse events reported with use of propranolol include bradycardia, hypotension, congestive heart failure, heart block, cardiac arrest, dyspnea, and cutaneous ulcers.

Early in vitro studies in the 1960's identified the presence of β receptors on the human uterus. In 1966, the first clinical studies demonstrated that administering IV propranolol to pregnant women at term caused increased contraction strength and frequency.² In 1996, the first clinical trial attempting to utilize propranolol as a labor augmentation agent was published. In this study, the authors demonstrated a nearly 50% reduction in the rate of CD among women with labor dystocia who were given IV propranolol compared to women with labor dystocia given placebo.³ Subsequently, there have been 5 additional studies examining propranolol as labor medication.⁴⁻⁸ One non-blinded RCT administered 2mg

of IV propranolol to nulliparous women admitted for labor or for induction of labor (IOL).⁸ Notably, these patients did not have any diagnosis of dystocia, and the medication was given as an adjunct to normal labor management. The CD rate was quite low overall in this study, and there was no significant difference between the two groups. Another study was a double-blind RCT of women with arrest of dilation, with an unchanged cervical exam for 2 hrs anywhere from 2-7cm during labor.⁷ Patients received 2mg IV propranolol with a repeat dose in 1 hr if unchanged, vs placebo. This study also had a low overall CD rate, with no difference between groups. Two additional studies have evaluated the use of propranolol as an induction agent.^{4,6} Both were done in Iran where the induction protocol is quite different than in the US. The first study, which included only nulliparous patients, showed no difference in CD rate but a 2.5 hour shorter time to delivery; the second study found a significant difference in CD rate from 40 to 20% in the PO propranolol group. Finally, one additional study evaluated the administration of propranolol to women with arrest of active phase but with a low rate of oxytocin usage – 28% of propranolol the group versus 60% of placebo group.⁵ Ultimately this study showed no difference in the CD rate, but given the low use of oxytocin in this study, it is less applicable to most obstetric practice. In the 7 total published clinical trials referenced above, there were no reported safety issues, side effects, or incidences of worse maternal or neonatal outcomes in those patients who received propranolol. Each of the 7 trials demonstrated the safety of administering this medication in labor.

The dose regimen in our proposal (2mg IV followed by up to one repeat dose \geq 2 hours later) is based on previous clinical trials of propranolol used in labor, as well as current accepted practice and propranolol dosing regimens used in other clinical scenarios. We believe that IV is more appropriate than PO in this context as the onset of action and half-life of the IV formulation is shorter than PO and more appropriate for the time frame of intended effect. According to the propranolol package insert, the usual dose is 1 to 3 mg, and the rate of administration should not exceed 1 mg per minute to diminish the possibility of lowering blood pressure. According to the labeling, a second dose may be given after two minutes. Our proposed protocol will be compliant with this recommendation.

1.3 Rationale

There is biologic plausibility for the role of propranolol in labor management. Prior studies have suggested possible benefit, but they have been small and heterogeneous with mixed results. The utility of propranolol in management of prolonged labor has not been established. This medication warrants further study to evaluate its effectiveness as an intervention for treatment of labor arrest.

2 STUDY AIMS

2.1 AIM 1: To compare CD rates among women given IV propranolol versus placebo for treatment of prolonged labor.

2.2 Endpoints

2.2.1 Primary Endpoint

- Mode of delivery (cesarean versus vaginal)

2.2.2 Secondary Endpoints

- Time (hours) from start of labor/IOL to delivery

- Time (hours) from study drug administration to delivery
- Time (hours) from start of second stage of labor to delivery
- Indication for CD
- Operative vaginal delivery
- Cumulative and maximum dose of intrapartum oxytocin received
- Postpartum hemorrhage
- Maternal blood transfusion
- Endometritis
- Chorioamnionitis
- Wound infection
- Other composite maternal morbidity: VTE, Hysterectomy, ICU admission, Maternal readmission within 7 days and 4 weeks, Maternal death
- ICN adm > 48 hours
- Composite neonatal outcome: neonatal blood transfusion, HIE, IVH grade 3 or 4, head cooling, severe RDS, NEC, Sepsis, Death

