8.1 Sample Size and Accrual

The sample size is based on the expected CD rate for women experiencing prolonged labor of approximately 45%. For a power of 80% and an alpha of 0.05, 326 women would be needed to find a decrease in rate of CD to 30%.

We estimate 40 eligible women deliver at HUP per month. We anticipate approaching 80% of these women or approximately 32 per month. With an estimated 50% consent rate, we would enroll approximately 16 women per month. Therefore, we would need 24 months to reach our target enrollment of 326 women.

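### The duration endpoints stop the clock at any delivery, cesarean included, so a difference in hours mixes labor speed with mode of delivery whenever cesarean rates differ; add time to vaginal delivery with cesarean as a competing event

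*Combined protocol and SAP*

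**What the plan says.** Section 2.2.2 lists three durations: "Time (hours) from start of labor/IOL to delivery", "Time (hours) from study drug administration to delivery" and "Time (hours) from start of second stage of labor to delivery". None is restricted by mode. Section 2.2.1 uses the word delivery for both modes: the primary endpoint is "Mode of delivery (cesarean versus vaginal"). A cesarean therefore ends each of these durations just as a vaginal birth does.

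The Study Summary plans a "two-sample t-test for continuous variables". Section 8.2 leaves the choice between a parametric and a non-parametric comparison open and includes every patient with follow-up. No section censors at cesarean, treats it as a competing event, or defines time to vaginal delivery.

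Section 8.1 expects a cesarean rate of about 45% and states that "326 women would be needed to find a decrease in rate of CD to 30" per cent. Section 3.4 leaves the indications for cesarean to the obstetric provider.

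The same list contains "Cumulative and maximum dose of intrapartum oxytocin received". Sections 3.1 and 4.3 make clear that every woman is on oxytocin before she receives study drug.

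**The concern.** Propranolol is tested as a treatment for prolonged labor, so readers will naturally take hours to delivery as a measure of how fast labor went. Section 1.2 invites that reading: it describes an earlier induction study that "showed no difference in CD rate but a 2.5 hour shorter time to delivery". There the two results could be read separately because the cesarean rates were alike. This trial is powered for unequal rates.

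If the drug averts cesareans, some women whose clock would have stopped at cesarean labor on to a vaginal birth. That can lengthen average hours even when vaginal birth is no slower. It can also cancel a real acceleration. At stake is the interpretation of secondary endpoints, not the primary result.

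Two neighboring endpoints need care for different reasons. Second-stage duration exists only for women who reach second stage, a subset formed after randomization. The oxytocin totals include dosing before study drug, which treatment cannot change, and a peak rate already reached cannot be lowered by anything given later.

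**Working it through.** **The plan's own figure.** Inputs from Sections 8.1 and 8.2: 45% versus 30%, power 80%, two-sided alpha 0.05. Assumed: 1:1 allocation, no dropout inflation.

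n per arm = [1.96√(2 × 0.375 × 0.625) + 0.8416√(0.45 × 0.55 + 0.30 × 0.70)]² / 0.15² = (1.342 + 0.569)² / 0.0225 ≈ 162.3, so 163 per arm and 326 in total. The stated figure reproduces.

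**How many clocks stop at cesarean.** 0.45 × 163 ≈ 73 on placebo and 0.30 × 163 ≈ 49 on propranolol. Vaginal births: about 90 and 114, or 204 in all.

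**Change in mode mix alone.** If mean time to each mode is the same in both arms, the difference in mean hours (propranolol minus placebo) is (0.30 − 0.45) × (mean time to cesarean − mean time to vaginal birth). For assumed gaps of −4 to +4 h this runs from +0.6 h to −0.6 h, so its sign depends on a quantity the documents do not give.

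**Competing hazards.** Let the placebo hazards be 0.55 (vaginal) and 0.45 (cesarean), constant, in units of one over the placebo mean time. The cesarean share is cesarean hazard / total hazard, and mean time is 1 / total hazard. Moving from 45% to 30% requires the cesarean-to-vaginal hazard ratio to change by the factor (0.30/0.70) / (0.45/0.55) = 0.524. That factor can be split between the two hazards on the log scale. Rejection rates are from simulated trials of 163 per arm and do not depend on the time unit.

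| Mechanism (cesarean 45% vs 30% in every row) | Vaginal hazard | Cesarean hazard | Mean time ratio | t-test on hours to any delivery |
|---|---|---|---|---|
| Only cesarean hazard falls | ×1.00 | ×0.52 | 1/(0.55 + 0.236) = 1.27 | longer in about 58%, shorter in 0% |
| One quarter via faster vaginal birth | ×1.18 | ×0.62 | 1.08 | longer in about 11% |
| Exact cancellation | ×1.27 | ×0.67 | 1/(0.70 + 0.30) = 1.00 | about 2.5% each way |
| One half via faster vaginal birth | ×1.38 | ×0.72 | 0.92 | longer in under 1%, shorter in about 10% |
| Only vaginal hazard rises | ×1.91 | ×1.00 | 1/(1.05 + 0.45) = 0.67 | shorter in about 95% |

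**What a cause-specific log-rank test for vaginal birth shows.** In the first row it rejects at about its nominal 2.5% each way, which is correct because vaginal speed is unchanged. In the cancellation row it finds faster vaginal birth in about 40%; Schoenfeld's formula agrees: Φ(√204 × ln 1.273 / 2 − 1.96) ≈ 41%. With one half it finds faster in about 62%.

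**Why not Gray's test or Fine-Gray alone.** In the first row a Gray-type test favors the drug in about 62% of trials although vaginal speed is unchanged. The cumulative incidence of vaginal birth ends at one minus the cesarean rate, so this test largely repeats the primary endpoint.

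**Sensitivity.**
- *Smaller effect.* At 45% versus 40% with only the cesarean hazard changing, the factor is (0.40/0.60) / (0.45/0.55) = 0.815, the mean ratio is 1/(0.55 + 0.367) = 1.09, and the t-test says longer in about 11%.
- *Non-constant hazards.* With a common Weibull shape k, the first-row mean ratio is 1.273^(1/k): 1.17, 1.13 and 1.08 for k = 1.5, 2 and 3. Rejection stays at 51% to 56%, but the shift in hours is much smaller than the 27% under constant hazards.

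**The case against.** Aim 1 concerns the cesarean rate only, and no section says that hours measure labor speed. The endpoints are named literally, and time to any delivery is a legitimate comparison of the randomized groups. A reader might infer from the first row of the table that this endpoint is invalid, or that the trial will probably report propranolol as prolonging labor. The documents support neither. That row assumes no effect on vaginal speed, whereas Sections 1.1 and 1.2 rest the rationale on stronger and more frequent contractions. If the drug acts wholly by speeding vaginal birth, the present endpoint works well.

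It is also true that 45% versus 30% is the alternative used for sizing, not a forecast. If the rates prove equal, the distortion from mode mix largely disappears. Mode of delivery and indication for cesarean will be reported beside the hours, and blinding limits arm-specific cesarean decisions. That providers control the timing of cesarean is an inference from their discretion over indications.

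These points lower the size of the concern and are accepted. They do not remove it. In the middle of the table, where the drug does speed vaginal birth, the t-test on hours finds little or nothing. Reporting the cesarean rate alongside does not tell a reader how much of a difference in hours comes from it.

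**Conclusion.** The point holds as a cheap improvement to secondary endpoints. Hours to any delivery combine labor speed and mode of delivery when cesarean rates differ, and the plan has no analysis that separates them. One cesarean benefit, 45% to 30%, is compatible with longer, equal or shorter hours.

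The percentages rest on 1:1 allocation, 163 per arm and constant hazards. They show what can happen and do not predict it: the 58% is the extreme case, and a modest share of faster vaginal birth or a smaller cesarean difference each bring it to about 11%. The documents give no durations, so neither the direction nor the size in hours can be stated for this trial.

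For oxytocin the point is qualitative. Dosing before study drug adds noise to the total and can hide an effect on the maximum, but the documents give no means, spreads or correlations from which to calculate a loss of power. The primary endpoint and the sample size are unaffected.

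**What to change.** In Sections 2.2.2 and 8.2:

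- Keep time to any delivery and label it as time until birth by any mode.
- Add time from study drug administration to vaginal delivery, with cesarean as a competing event. Section 5.3 already has the dose time recorded, so no new time origin is needed. Any woman randomized but never dosed stays in the analysis, counted from assignment.
- Report the cumulative incidence of vaginal and of cesarean delivery by arm, together with the cause-specific hazard ratio for vaginal delivery. Do not rely on Gray's test or Fine-Gray alone.
- Count cumulative and maximum oxytocin from study drug administration onward, or adjust for the dose already received.
- Label second-stage duration as a descriptive comparison in a post-randomization subset. The competing-event analysis does not cure that selection.

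The cost is a short amendment, a less familiar summary than mean hours, and possibly a case report form field for oxytocin at dosing. Some selection remains in the cause-specific ratio: if cesareans concentrate in slower women, its log-rank test wrongly said slower in 4% to 9% of simulated trials (2.5% nominal, assumed spreads), while the t-test on hours said longer in 71% to 86%. No additional women are needed.

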3.4 Ensuring Necessary Medical Interventions

Enrollment in this study will not alter any aspects of routine labor management. Continuous EFM and tocometry will occur on all patients in labor, consistent with standard of care. The remainder of clinical care in labor will be at the covering OB providers' discretion. The frequency and timing of cervical examinations will occur per provider discretion. Standard treatment for GBS positive and GBS unknown patients will occur. The use of internal fetal monitoring and intrauterine pressure catheter will be at the discretion of the OB provider. Standard obstetric indications for cesarean delivery will be also be at the discretion of the OB provider. There will be no additional blood draws or cervical examinations for women enrolled in this study.

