5.2 Randomization

Eligible, consented women will receive pre-randomized study medication. Study medications will be prepared and randomized by the Investigational Drug Service (IDS) via a random generated randomization scheme. The randomization scheme will be generated by a pharmacy associate within IDS not involved in the clinical care of the patient. Two single-use vials of the same medication – either propranolol or placebo- will be included in a numbered bag. One vial will be used for the first dose. If a patient meets eligibility criteria to receive a repeat dose, the second vial in the same bag will be used.

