8.2 Data Analyses Plans

Measures of relative risk will include 95% confidence intervals. Descriptive statistics will be presented as mean with standard deviation, median with interquartile range, or proportion with 95% confidence interval based on data type and distribution. Comparisons between groups will be performed using a Chi-square or Fisher's exact test for categorical variables and parametric or non-parametric tests for continuous variables, as appropriate. Intention-to-treat analyses will be conducted such that all patients with available follow-up measures will be included in the analysis. Statistical analyses were conducted in STATA, version 15.1 (College Station, Texas). Two-tailed P values of <0.05 will be considered statistically significant.

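### The secondary endpoint on cesarean indication has no denominator and defaults to women who had a cesarean, where fewer arrest cesareans can look like an excess of fetal indications

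*Combined protocol and SAP*

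**What the plan says.** Section 2.2.2 lists "Indication for CD" among 14 secondary endpoints and adds nothing on categories, denominator or summary measure. Section 3.4 leaves the decision to the treating team: "Standard obstetric indications for cesarean delivery will be also be at the discretion of the OB provider". No section sets study categories for the recorded reason.

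Section 8.2 gives one general rule: "Comparisons between groups will be performed using a Chi-square or Fisher's exact test for categorical variables". It promises 95% confidence intervals for relative risks and describes intention-to-treat analysis as including every patient whose follow-up measure is available. It does not say how to treat a variable that has no value for women delivered vaginally.

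Cesarean itself is the primary endpoint (2.2.1). In 8.1, "The sample size is based on the expected CD rate for women experiencing prolonged labor of approximately 45" percent, and "326 women would be needed to find a decrease in rate of CD to 30" percent. Section 1.1 presents propranolol as a candidate treatment for labor arrest.

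**The concern.** A woman delivered vaginally has no indication. Applied as written, 8.2 therefore leads to a test among women who had a cesarean. The trial is sized on the expectation that this group will be a third smaller on propranolol, and the rationale in 1.1 implies that the missing women would mostly have had arrest cesareans. Randomization does not protect a comparison within a subset that treatment is meant to change.

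Two questions are at stake: whether the drug reduces the cesareans it is aimed at, and whether it adds cesareans for fetal status. The second is a natural question for a drug that, according to 1.2, increases contraction strength and frequency. The mix within cesareans answers neither cleanly. If the drug works on arrest alone, the fetal share rises on propranolol and can be reported as a fetal safety signal.

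**Working it through.** **Inputs from the documents.** Cesarean 45% on placebo and 30% on propranolol (8.1); "For a power of 80% and an alpha of 0.05" (8.1); "Two-tailed P values of <0.05 will be considered statistically significant" (8.2).

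**Assumptions.** Allocation is 1:1, since 5.2 says only "via a random generated randomization scheme". There is no dropout, since 8.1 states no inflation. The risk *f* of a fetal-indication cesarean per randomized woman is not in the documents; it is taken as 5% to 20%, equal in both arms. All other cesareans count as arrest cesareans, and all averted cesareans are arrest cesareans.

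**Step 1: the plan's own figure.** With pooled variance under the null and no continuity correction,

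n per arm = [1.96·√(2·0.375·0.625) + 0.8416·√(0.45·0.55 + 0.30·0.70)]² / 0.15² = (1.342 + 0.569)² / 0.0225 ≈ 162.3.

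This rounds up to 163 per arm, 326 in total, as stated. Power at 163 per arm is 80.2%.

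**Step 2: the subset.** Expected cesareans are 0.45 × 163 = 73.35 on placebo and 0.30 × 163 = 48.9 on propranolol.

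**Step 3: the shift in share.** The fetal share of cesareans is f/0.45 on placebo and f/0.30 on propranolol. The ratio is 0.45/0.30 = 1.50 whatever the value of f. Per randomized woman the difference is f − f = 0.

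**Step 4: how often this yields a false signal.** In 200,000 simulated trials per row, with 163 per arm, a Pearson chi-square test (z > 1.96 towards propranolol) was applied to both denominators. The nominal rate in that direction is 2.5%.

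| Assumed f | Fetal share, placebo | Fetal share, propranolol | False excess, within cesareans | False excess, all randomized |
|---|---|---|---|---|
| 5% | 11.1% | 16.7% | 15% | 2.4% |
| 7.5% | 16.7% | 25.0% | 21% | 2.5% |
| 10% | 22.2% | 33.3% | 28% | 2.5% |
| 15% | 33.3% | 50.0% | 46% | 2.4% |
| 20% | 44.4% | 66.7% | 68% | 2.5% |

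The propranolol share is numerically higher in 80% to 99% of trials. For example, at f = 15% both arms expect 24.4 fetal-indication cesareans, while arrest cesareans go from 48.9 to 24.4.

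**Step 5: a real rise.** Hold arrest at 34% in both arms and let fetal-indication cesareans go from 11% to 20% (assumed). The share goes from 0.11/0.45 = 24.4% to 0.20/0.54 = 37.0%. It is higher on propranolol in 96% of simulated trials. The rise is significant in about 41% within cesareans, against 62% over all randomized women.

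**Step 6: the target effect.** Under the step 4 assumptions, arrest cesarean over all randomized women has 83% to 95% power.

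**Step 7: when the share does not move.** If both types fall in proportion, for example fetal from 15% to 10% while the total falls from 45% to 30%, the share stays at 33.3%.

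**The case against.** The strongest reply is that the plan never commits to a within-cesarean comparison. A reader might infer from 8.2 that it does, but the text only names tests for categorical variables in general. A relative risk for each indication over all randomized women, or a variable with a no-cesarean level, would fit the same words. This stands: the defect is an open denominator with an unfavorable default, not a chosen flawed analysis. It remains a defect, because the denominator could be settled after the results are seen.

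A reader might also infer that the mix could hide a real rise in fetal-indication cesareans. It does not if arrest cesareans are constant, because the share must then rise too; step 5 shows a loss of power, not concealment. Nor does every benefit read as harm, since step 7 shows that proportional falls leave the share unchanged. The 1.5-fold figure is the extreme case, in which arrest accounts for the whole reduction.

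Single expected tables also look mild. With 13, 18 or 24 fetal-indication cesareans in each arm, out of 73 and 49 cesareans, chi-square gives p = 0.25, 0.15 and 0.074. That is correct, but it describes the average table and not how often a trial crosses 0.05, which step 4 gives.

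Finally, the endpoint is secondary and feeds no interim analysis (9.4.1) or sample size. The neonatal composite and intensive care nursery admission also bear on fetal harm. If counts by indication were published beside the arm sizes, readers could recompute the risks. All of this limits the consequence. None of those other endpoints says why a cesarean was done.

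**Conclusion.** The point holds in a limited form. The endpoint has no denominator, and the general rule in 8.2 defaults to women who had a cesarean. On that default, a fall concentrated in arrest cesareans raises the fetal share by up to 1.5-fold with no added fetal-indication cesarean, and gives a nominally significant false excess in about 15% to 68% of trials instead of 2.5%.

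The 1.5-fold figure rests on the plan's 45% and 30% and on all averted cesareans being for arrest. The false-signal range rests also on 1:1 allocation and on an assumed fetal-indication risk of 5% to 20%, equal in both arms. The direction needs only that arrest cesareans fall proportionally more than fetal-indication ones, which the rationale in 1.1 implies but does not guarantee.

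The primary endpoint and the 326 women are unaffected. The change is worth making before unblinding, but the trial does not depend on it.

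**What to change.** In 2.2.2, replace the endpoint with two: cesarean for labor arrest (yes/no) and cesarean for non-reassuring fetal status (yes/no), each over all randomized women, with women delivered vaginally counted as no. Report each with a relative risk and 95% confidence interval under 8.2.

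Assign each cesarean one primary recorded indication. Because the indication comes from the treating provider, state a rule for cesareans that list both arrest and fetal status, and fix it before unblinding; without it the two endpoints stay ambiguous. Report the mix of indications within cesareans descriptively, without a test.

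The cost is one classification rule and two lines of analysis. The listed endpoint already requires the indication to be recorded, so no patients, visits or procedures are added and labor management does not change.
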